9.1 Study Design – General Aspects

The effectiveness objectives will be addressed through a retrospective cohort study using linked secondary databases in England accessed through ORCHID and NHS Digital's TRE. Persons vaccinated with Oxford/AstraZeneca COVID-19 vaccine or another COVID-19 vaccine will be compared to matched persons not vaccinated with any COVID-19 vaccine for occurrence of study outcomes.

Due to England's vaccination campaign starting with the older age group, as of March 22 2021, over 90% of people 70 years of age or older were vaccinated with at least one dose of any COVID-19 vaccine (Public Health England, 2021). Therefore, it is expected that the concurrent control arm will have considerable challenges. A greater proportion of younger people might be included who may have lower hospitalization and death (particularly because the Joint Committee of Vaccination and Immunisation (JCVI) recommended early vaccination of people 16 to 64 years with comorbidities). Additionally, people receiving terminal care and those who do not engage much with the health system may also be included. For these reasons, the concurrent control arm is matched with the vaccine arm by age and other characteristics. Events' rates will also be stratified by age groups (e.g. 12-15,16-49, 50-64, 65-69, 70-79, 80+).

We will also explore how COVID-19 vaccination in England coincided with the 3rd wave of COVID-19 and any subsequent wave that may occur. For this analysis, we will include vaccination data periods beyond February 2021.

There have been changes in the age groups vaccinated and the introduction of booster doses. The Moderna and Pfizer BioNTech vaccines have been licenced for children (Medicines and Healthcare products Regulatory Agency (a & b), 2021) and booster doses were introduced in the autumn of 2021. For these reasons the analyses will be extended to include the 12–16-year-old age-group and any booster vaccination (9)(Department of Health and Social Care, 2021). Finally, the UK COG has centralised data on COVID-19 variants allowing VE to reported by variant.

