9.2.3 Exclusion Criteria

People who meet the following criteria will be excluded:

• Primary analysis: People with a history of COVID-19 infection (confirmed by reverse transcriptase polymerase chain reaction (RT-PCR) or not) prior to vaccination. This group of people is not excluded in the sensitivity analysis.

A sensitivity analysis excluding persons living in an elderly care home will be considered.

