9.7 Data Analysis

9.7.1 Statistical Methods – General Aspects

A detailed SAP will be developed for this analysis. The SAP may modify the plans outlined in the protocol; any major modifications of primary endpoint definitions or their analyses would be reflected in a protocol amendment. For all study designs, p-values will be quoted to two decimal places, unless they are less than 0.001 (whereby the p-value will be given as < 0.001) or between < 0.005 and > 0.001, in which case they will be stated to three decimal places. Parameter estimates will be reported with 95% CIs. All statistical tests are 2 sided and with a 5% significance level.

A CONSORT 2010 Flow Diagram of the study population detailing each step of the inclusion and exclusion criteria applied will be generated. As indicated in section 9.4, to obtain the most followup data, the primary analysis will include all HES data until 8 weeks prior and all raw hospitalization data (SUS) from 8 weeks to 2 weeks prior database lock. A sensitivity analysis including only HES data, therefore a shorter follow-up for hospitalization, will also be done.

For the concurrent control arm, each week starting from 8th December 2020, we will match all newly vaccinated persons in a 1:1 ratio to unvaccinated controls (Dagan et al, 2021). Newly vaccinated persons will be eligible for inclusion in the study, even if they will have previously been selected as a control. We will match vaccine recipients and controls on variables associated with the probability of both vaccination and infection or severity of COVID-19: age (study defined age bands), gender, general practice, (or NHS Region), and comorbidity as defined by CMMS quartile. We will exact match each week (if feasible). To assess the quality of matching, love plots will be created showing the mean standardized difference between each vaccinated cohort (AstraZeneca or other vaccine cohort) and the comparator cohorts in participants' characteristics. If important differences are observed, the matching criteria will be refined.

The demographic and characteristics of study participants in each vaccine arm and its respective control arm at baseline will be determined during the 12-month period before index date using the measurement closest to index date.

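### Section 9.1 answers the possible presence of terminal-care patients among controls with matching, but nothing in the plan identifies them, so VE against death can be inflated

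*Protocol*

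**What the plan says.** Protocol section 9.1 expects difficulties with the concurrent control arm because uptake in older people was already high. It lists who may be left in that arm: younger people, and then "Additionally, people receiving terminal care and those who do not engage much with the health system may also be included". The next step in the argument is "For these reasons, the concurrent control arm is matched with the vaccine arm by age and other characteristics".

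Section 9.7.1 fixes the matching variables as "age (study defined age bands), gender, general practice, (or NHS Region), and comorbidity as defined by CMMS quartile". Matching is weekly from 8 December 2020, "in a 1:1 ratio to unvaccinated controls".

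Section 9.2.3 has one exclusion for the primary analysis: "People with a history of COVID-19 infection", where the infection came before vaccination. It adds: "A sensitivity analysis excluding persons living in an elderly care home will be considered". Section 9.7.3 shows that this rests on a proxy from household size and average age.

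The Poisson model in 9.7.1 adjusts for the matching variables, BMI, smoking, prescribed medications and frailty score. Table 6 in 9.3.3 reduces medication to immunosuppressant or not, and limits the frailty index to people aged 65 and over.

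Under 9.3.2, COVID-19 related death is a primary outcome and all-cause mortality a secondary one. An event within 28 days of a positive RT-PCR counts as COVID-19 related.

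**The concern.** The protocol names a problem and gives a response that does not reach it. Someone near the end of life and someone stable with several chronic conditions can share an age band, gender, practice and CMMS quartile. Matching on those four variables treats them as exchangeable, although their short-term risk of death differs greatly.

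If people in terminal care are vaccinated less often than others of their age, they make up a larger share of controls than of vaccinees. Their deaths then lower the apparent death rate in the vaccine arm relative to control, whatever the vaccine does. All-cause mortality is affected directly. COVID-19 death is affected through the 28-day rule, because a death from the terminal illness after a positive test is a primary event.

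The planned love plots compare measured characteristics only, and no terminal-care variable is listed, so the balance check would not show this imbalance. Section 9.11.1, to which the ENCePP checklist points for selection bias, acknowledges that people who choose vaccination may differ from those who do not, but singles out only age adjustment as critical. Section 9.9 does not return to the matter.

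**Working it through.** The documents give no figure for this group and no power calculation, so there is no plan figure to reproduce. The calculation below shows what could follow at age 80+.

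**Input from the protocol.** Uptake U = 91% at age 80 and over as of 7 April 2021 (section 9.5), so 9% were unvaccinated.

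**Assumed inputs.** t, the share of the age group in terminal care; q, final uptake among them; m, their 90-day mortality; 2.5% 90-day mortality in everyone else; no true vaccine effect on all-cause death; no benefit from CMMS or frailty adjustment.

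**Formulas.**
- Terminal share of controls: c = t(1 − q)/(1 − U)
- Terminal share of vaccinees: v = tq/U
- 90-day risk in an arm: share × m + (1 − share) × 0.025
- Spurious VE = 1 − risk(vaccinees)/risk(controls)

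**Results with the pool held at 91% coverage.**

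| t | q | m | c | v | risk, controls | risk, vaccinees | spurious VE |
|---|---|---|---|---|---|---|---|
| 0.2% | 80% | 25% | 0.44% | 0.18% | 2.60% | 2.54% | 2% |
| 0.5% | 75% | 30% | 1.39% | 0.41% | 2.88% | 2.61% | 9% |
| 1% | 50% | 50% | 5.56% | 0.55% | 5.14% | 2.76% | 46% |
| 2% | 50% | 50% | 11.1% | 1.10% | 7.78% | 3.02% | 61% |

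Over the 12 combinations of t = 0.5, 1, 2%; q = 50, 75%; m = 30, 50%, the range is 9% to 61% and the median 29%. If uptake among the terminally ill is also 91%, then c = v and there is no bias.

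**Effect of the weekly rollout.** Matching starts when almost nobody is vaccinated. At coverage k, with uptake growing proportionally in both groups, the terminal share of controls is t(1 − qk/U)/(1 − k). For t = 1%, q = 50%, m = 50%:
- At the start, c = 1%, control risk is 2.975%, and spurious VE is 1 − 2.761/2.975 = 7%.
- Averaged over k from 0 to 91%, c = 1.74%, control risk is 3.33%, and spurious VE is 1 − 2.761/3.327 = 17%.
- Over the same 12 combinations the averaged values run from 2% to 27%.

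Follow-up of a vaccinee ends when the matched control is vaccinated (9.2.4). Person-time therefore concentrates in pairs whose control stays unvaccinated, which pushes these averaged values back up.

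**With a real vaccine effect.** Observed RR = (1 − true VE) × bias factor. In the 46% row the factor is 2.761/5.139 = 0.537, so a true VE of 50% reads 1 − 0.5 × 0.537 = 73%, and 80% reads 89%.

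**Opposing group.** Suppose low engagers are 40% of controls and 5% of vaccinees, with half the recorded event rate. Suppose terminal patients are 1% of controls and 0.5% of vaccinees, with 20 times the rate. Relative to everyone else:
- Vaccinees: 1 + 0.005 × 19 − 0.05 × 0.5 = 1.07
- Controls: 1 + 0.01 × 19 − 0.40 × 0.5 = 0.99
- Factor: 1.07/0.99 = 1.08, so a true VE of 50% reads 46%

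With 3% of controls terminal, the control value is 1.37, the factor 0.78, and 50% reads 61%.

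**After the fix.** With terminal patients out of both arms, c = v = 0 and the factor for this mechanism is 1.00.

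**The case against.** The plan is not without defences. Frailty adjustment covers ages 65 and over, where the concern is greatest, and CMMS quartile is both matched and adjusted for. Section 9.7.1 allows the matching criteria to be refined. Section 9.3.1 counts a person as one-dose vaccinated only from day 22, which, if applied to the event count, weakens the argument that vaccinees were well enough to attend on the index date. A care-home sensitivity analysis and early post-dose windows are also mentioned. These are fair points, and the figures above take no credit for them. They reduce the problem without removing it: none identifies terminal care, and below age 65 there is no frailty score at all.

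A reader might infer that the protocol predicts such patients will accumulate among controls and that VE is therefore inflated for every outcome. The documents do not support that. Section 9.1 says only that they may be included, and it openly expects considerable challenges. For hospitalization and ICU admission the sign depends on whether terminal patients are admitted more or less often than others, which the documents do not say; if not more often, there is no upward bias from this source. The low engagers named in the same sentence can pull VE down.

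A reader might also take 46% as a central estimate. It is the third highest of the 12 combinations, uses the less favourable value of both uptake and mortality, and assumes a pool fixed at its April 2021 composition.

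**Conclusion.** The point holds as a mismatch between a stated problem and its stated remedy. Section 9.1 raises terminal care and responds with matching, yet no matching variable, exclusion or listed covariate identifies it. Residual confounding remains that can inflate VE, chiefly against all-cause death and death within 28 days of a positive test.

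Its size is not documented. Spurious VE against all-cause death at age 80+ runs from about 2% to about 60%, resting on assumed prevalence, uptake and mortality. The upper end also needs a static 91% pool and no gain from CMMS or frailty adjustment. No net direction is claimed for hospitalization or ICU admission. This is a design weakness worth correcting because the correction is cheap; it does not show that the study's VE estimates will be wrong by a known amount.

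**What to change.** 1. In 9.2.3, exclude from both arms, at the index date, people with a palliative or end-of-life care code recorded before that date (ORCHID and HES, and GDPPR if the codes exist there). Preferably also exclude people who are hospital inpatients on that date (HES, or SUS where linked to ORCHID). The inpatient rule is a further safeguard and does not follow directly from the statement in 9.1.
2. Report the analysis without these exclusions as a sensitivity analysis in 9.7.3.
3. Use the 0-7 and 8-14 day post-dose windows already listed in 9.7.2 as a check: a marked apparent benefit against death that early would point to residual confounding.
4. Reword 9.1 so that matching on age and other characteristics is not presented as the response to terminal care, and note the residual problem, including low engagers, in 9.9 or 9.11.1.

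The cost is one code list, one admission-date check in data the protocol already plans to link, and protocol wording. Code availability in GDPPR must be confirmed, since 9.4 says its clinical concepts are restricted. The downside is that VE would no longer apply to people in terminal care, and a small share of persons would be lost.

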9.2 Setting

9.2.1 Study Population

The study population of this study is people in England who have received at least one dose of the Oxford/AstraZeneca COVID-19 vaccine from January 2021 onwards (the AstraZeneca vaccine arm) or at least one dose of another (e.g. mRNA) COVID-19 vaccine from December 2020 onwards (the Other vaccine arm) and people in England who were not vaccinated with any COVID-19 vaccine during the same time period (concurrent control arm) who will be matched to the vaccinated individuals by age, gender, GP practice (NHS region), and comorbidity (see Section

9.7.1 for a description of matching). Study participants of any age will be considered. For the vaccinated individuals, the study's index date is the date of vaccination of the 1st dose.

Concurrent controls who become vaccinated will be censored at date of vaccination and, then may re-enter the study as newly vaccinated individuals. An appropriate control group will be identified for the booster dose evaluation.

To contextualize, we will describe the impact of SARS-CoV2 on the unvaccinated English population, prior to the availability of COVID-19 vaccines. We will conduct a descriptive analysis of COVID-19 of this historical population of unvaccinated persons in England.

9.2.2 Inclusion Criteria

The study population is required to meet the following inclusion criteria:

1. For the vaccinated arms:

- Any COVID-19 vaccination at the index date
- Have continuous data coverage for the COVID-19 infection datasets, i.e. Second Generation Surveillance System (SGSS) and National Pathology Exchange (NPEX) from their initiation for history of prior COVID-19 infection
- Have continuous data coverage in other linked databases for a minimum of 12 months prior to the index date for assessment of baseline variables including socio-economic status, comorbidities, and follow-up of outcome events.

2. For the control arms:

- Eligible for any COVID-19 vaccination based on age at the index date for the concurrent control individuals.
- Have continuous data coverage for the COVID-19 infection datasets, i.e. SGSS and NPEX from their initiation for history of prior COVID-19 infection
- Have continuous data coverage in other linked databases for a minimum of 12 months prior to the index date for assessment of baseline variables including socio-economic status, comorbidities, and follow-up of outcome events.
- People who have not (yet) received any COVID-19 vaccine (Oxford/AstraZeneca, Pfizer, or Moderna COVID-19 vaccine) recorded in their GP record or in NIMS. They will be used as concurrent controls. However, they will be censored at date of vaccination and, then may re-enter the study as newly vaccinated individuals.

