3. RESPONSIBLE PARTIES

Name	Professional title	Role in study	Affiliation	Email address

Name	Professional title	Role in study	Affiliation	Email address

4. **PROTOCOL SYNOPSIS**

Background/Rationale: The United Kingdom (UK) is one of the first countries that introduced a mass vaccination campaign for COVID-19 and vaccination of the adult population first focused on the oldest age groups, their carers and health care workers (JCVI, 2020). Three COVID-19 vaccines were licensed and are being used including the Moderna, the BioNTech/Pfizer, and the Oxford/AstraZeneca vaccines. Vaccination with the BioNTech/Pfizer vaccine started in December 2020 and the Oxford/AstraZeneca vaccine started in early January 2021. This study is to primarily assess the effectiveness of the Oxford/AstraZeneca COVID-19 vaccine. Given the known high efficacy of the mRNA vaccines in randomized controlled trials (RCTs) and real-world evidence studies, the study aims also to evaluate the vaccine effectiveness (VE) of other COVID-19 vaccines as a validation of the study's methods. On 16 September 2021 it was announced that Booster doses would be introduced in the UK to address vaccine waning and for groups with a suboptimal response. Little is known about health care resource utilisation (HCRU) and health care costs for those who have had COVID-19 or by individual clinical risk group. The RAVEN study is a retrospective cohort study to assess the real-world effectiveness of the Oxford/AstraZeneca COVID-19 vaccine in England. The study is using linkage of the English national databases on COVID-19 vaccination, testing, medical records, hospitalization, and death. Analyses will examine the effectiveness of one and two doses, and booster or other additional doses if applicable. This study's extension (October 2021) adds a more detailed exploration of VE in risk groups and an evaluation of the HCRU by people with COVID-19 compared with those who are vaccinated.

Research question and objectives:

Primary: To assess the real-world effectiveness of the Oxford/AstraZeneca COVID-19 vaccine among people who receive at least one dose of the vaccine, overall, and by number of doses, by age group, by comorbidity status, by time period after each dose, by interval between doses.

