Secondary: To assess the real-world effectiveness of other COVID-19 vaccines in people vaccinated who received at least one dose; overall, and by number of doses, by age group, by comorbidity status, by time period after each dose, and by interval between the doses.

RAVEN extension objectives:

- 1. To describe the risk profile of the population at risk due to being ineligible for COVID-19 vaccines due to having suboptimal vaccine response (and thus more likely to have a breakthrough case), predict breakthrough cases and their time to vaccine waning, and describe the predictors of accepting AZ boosters. People who are immunocompromised are the primary population of interest, in our exploration of suboptimal vaccine response.
- 2. To conduct an analysis of COVID-19 and long COVID HCRU and health care cost for the whole population and for risk groups identified as having a suboptimal vaccine response.

- 3. To explore VE against the different SARS-CoV-2 variants.
- 4. To assess the effectiveness of the Oxford/AstraZeneca COVID-19 vaccine against any positive SARS-CoV-2 test, medically attended COVID-19 and rate of emergency department visit associated with COVID-19.
- 5. To assess the effectiveness of the Oxford/AstraZeneca COVID-19 vaccine and other COVID-19 vaccines in people vaccinated with booster/other additional doses.
- 6. To assess the effectiveness of heterologous dosing (including at least one Oxford/AstraZeneca COVID-19 vaccine)
- 7. To estimate the impact of vaccination on household incidence/transmission
- 8. To estimate the impact of vaccination on long COVID

Methods:

Study design: Secondary data analysis using a retrospective cohort design

Population: The study population is people in England who have received at least one dose of the Oxford/AstraZeneca COVID-19 vaccine (the AstraZeneca vaccine arm) or at least one dose of other COVID-19 vaccines (the other COVID-19 vaccine arm) and people in England who were not vaccinated with any COVID-19 vaccine during the same time period (concurrent control arm). All study participants are eligible for COVID-19 vaccination based on age.

Variables

Exposure(s): The main exposure is whether a person was vaccinated with the Oxford/AstraZeneca COVID-19 vaccine or with any other COVID-19 vaccine versus not vaccinated with any COVID-19 vaccine.

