9.5 Study Size

The NHS Digital database comprises data from the national registries of vaccination and hospitalization with linkage to the CMR, lab, and mortality data. It is the largest dataset possible for England and covers all regions. As of early March 2021, near 20 million people in England have been vaccinated with at least 1 dose of any COVID-19 vaccines. According to a recent study in Scotland (Vasileiou et al 2021), the Oxford/AstraZeneca vaccine have been used by the majority of the 75+ years old age group and by a significant proportion of the 60-65- and 70-75-years old age groups.

Based on the preliminary count of the cohort of VE from ORCHID in collaboration with PHE (N=5.4 million), as of 7/4/2021, 42.1% of the population have received a COVID-19 vaccine. Overall, 91% of people 80 years and older, 91% of people 65-79 years old, and 79% of people aged 16-64 years old in risk groups were vaccinated. Of those vaccinated, 38% has received the Oxford/AstraZeneca COVID-19 vaccine, i.e. more than 7 million people. It is expected that almost all of England's COVID-19 vaccination data are included in the NHS Digital databases representing the best option for this type of study. Given a large number of people vaccinated with the Oxford/AstraZeneca COVID-19 vaccine and the use of the national database, the study should have sufficient power to address the study objectives.

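### Control eligibility rests on age alone, is undefined and is stated differently for the two arms, although vaccination was also offered by comorbidity and occupation; this puts VE by comorbidity at risk

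*Protocol*

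**What the plan says.** Section 9.2.2 sets different entry rules. The vaccinated arms need "Any COVID-19 vaccination at the index date" plus data coverage. The control arm needs the same data coverage, no recorded COVID-19 vaccine, and to be "Eligible for any COVID-19 vaccination based on age at the index date for the concurrent control individuals".

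Other places describe the population differently. The synopsis (Section 4) says "All study participants are eligible for COVID-19 vaccination based on age". Section 9.2.1 says "Study participants of any age will be considered". Section 9.7.2 lists a possible stratum under 12 years, whereas Section 9.1 extends the analysis only to ages 12–16.

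The protocol does not describe a roll-out by age alone. According to the synopsis, "vaccination of the adult population first focused on the oldest age groups, their carers and health care workers". Section 9.1 adds that the national committee "recommended early vaccination of people 16 to 64 years with comorbidities". Section 9.5 reports that by 7 April 2021 "79% of people aged 16-64 years old in risk groups were vaccinated".

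Under Section 9.7.1, newly vaccinated people are matched 1:1 each week from 8 December 2020 on age band, gender, practice or NHS region, and quartile of the Cambridge Multimorbidity Score (CMMS). Balance is checked with love plots. The Poisson model adjusts for the matching variables, BMI, smoking, prescribed medications and frailty score.

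**The concern.** The weekly matched design works if each control could have been vaccinated in the same week as the vaccinee and resembles that person in the reasons for vaccination. An age-only rule does not describe who could be vaccinated in a given week, because the protocol names two other routes. The phrase is not defined either: it can mean the age group being invited that week, or any age at which a vaccine could be given. Two analysts could build different matched cohorts from the same text.

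VE by comorbidity status is part of the primary objective, and immunocompromised people are the primary population of interest in the extension's work on suboptimal response. Younger people in clinical risk groups are the ones whose controls depend most on this wording.

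**Working it through.** The protocol gives no figure to reproduce here. The check sets the passages side by side and adds an illustration whose inputs are assumptions.

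**1. Do the passages agree?** Section 9.2.2 applies age eligibility to controls only; the synopsis applies it to both arms. If it means the age invited that week, the synopsis sentence is untrue for anyone vaccinated early for comorbidity or occupation. If it means a minimum vaccine age, the synopsis and Section 9.2.2 largely agree. Considering people of any age can still be followed by an eligibility rule, but a stratum under 12 then needs explaining.

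**2. Age group invited that week.** Let T be the youngest invited age (an assumption; the protocol gives no opening dates). The share of single-year ages in a band that can supply controls is the number of ages at or above T, divided by the number of ages in the band:

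- 16–49 (34 ages): T = 50 or above gives 0/34 = 0%; T = 40 gives 10/34 = 29%.
- 50–64 (15 ages): T = 65 or above gives 0%; T = 60 gives 5/15 = 33%; T = 55 gives 10/15 = 67%.

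At 0%, a vaccinee in that band has no eligible control under exact age-band matching, and an equally comorbid unvaccinated person of the same age is barred. At a partial share, controls are older than vaccinees who span the band.

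To see the direction and possible size, assume uniform ages in the band, vaccinees across the whole band, controls only at T or above, event risk multiplied by g per decade with g from 1.5 to 2.5, and no age adjustment within the band. Then

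factor on the rate ratio = mean of g^(age/10) over the band ÷ mean of g^(age/10) over ages ≥ T,

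apparent VE = 1 − (1 − true VE) × factor.

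| Band, T | Factor (g = 1.5 to 2.5) | True VE 50% appears as | True VE 80% appears as |
|---|---|---|---|
| 50–64, T = 60 | 0.83 to 0.68 | 58.6% to 66.1% | 83.4% to 86.5% |
| 50–64, T = 55 | 0.91 to 0.83 | 54.4% to 58.5% | 81.8% to 83.4% |
| 16–49, T = 40 | 0.66 to 0.47 | 67.0% to 76.6% | 86.8% to 90.6% |

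The bias favours the vaccine. Finer age adjustment in the model would reduce it.

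**3. Minimum age for any vaccine.** With T = 16, every age in each band from 16 upwards qualifies. With T = 18, 32/34 = 94% of 16–49 and 100% of the older bands qualify. The loss in step 2 largely disappears.

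The remaining question is comorbidity. A person aged 16–64 vaccinated early for a priority condition is matched to someone in the same CMMS quartile, who need not have any priority condition. The model's other terms cover this only in part. In Table 6, prescribed medication is immunosuppressant or not, BMI is obese or not, and the frailty index exists only from age 65. Most of the priority conditions in Table 6 therefore enter only through the score. If a share p_V of vaccinees and p_C of controls in a matching cell have a priority condition that multiplies risk by c, the rate ratio is multiplied by

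[1 + p_V(c − 1)] ÷ [1 + p_C(c − 1)].

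With p_V above p_C and c above 1, this exceeds 1 and VE is understated. The documents give none of the three quantities.

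**The case against.** The strongest reply is that the text leans towards the minimum-age reading. The amendment history explains the updated inclusion criteria by people under 16 having become eligible, and Section 9.1 ties the younger ages to licensing. Section 9.2.2 mentions no invitation cohort. On that reading an age condition is needed only for controls, and an immunosuppressed unvaccinated 40-year-old is not barred. This stands as the likelier intention, but the protocol does not say so.

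Second, the plan has safeguards: matching on four variables, adjustment for prescribed medications, and love plots that can lead to refined matching. Strata for specific conditions can be formed in both arms, so that people with a condition are compared with each other. These do reduce the problem. However, balance checks act only on what is plotted and after the fact, and a condition-specific stratum breaks the matched pairs, since a vaccinee's control need not share the condition.

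Third, restricting controls to people already offered vaccine would push the pool towards those who declined or are disengaged, a worry that Sections 9.1 and 9.11.1 raise. That counts against a narrower control pool. It does not count against admitting controls by risk group as well as by age.

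A reader might also infer from the 79% uptake in risk groups aged 16–64 that about four in five of them would go without a control. The documents do not support this. The 79% is uptake, not a share left unmatched. The inference needs the invited-age reading, assumed opening dates for younger ages, and even uptake across 16–64.

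**Conclusion.** Two things are certain from the text: the eligibility statements in the synopsis and Sections 9.2.1 and 9.2.2 are not aligned, and the key phrase is undefined in a roll-out that the protocol says was not by age alone.

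The consequence depends on the reading. Under the invited-age reading, people vaccinated early for comorbidity lose their proper controls, which costs representativeness and precision in younger comorbid strata; VE is inflated where the threshold cuts an age band. Under the minimum-age reading, few adult controls are lost, and what remains is possible confounding by indication within CMMS quartile.

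The size of either effect cannot be derived from the documents; the table above shows direction and scale under its stated assumptions only. It would go too far to conclude that VE by comorbidity is invalid: that is a conditional risk, and existing matching, adjustment and balance checks limit it. It still deserves correction before the matched cohort is built, because it touches a component of the primary objective and costs little.

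**What to change.** 1. State one eligibility rule for both arms and define age eligibility explicitly. Under it, an unvaccinated person eligible by age or by clinical risk group (the Table 6 conditions) at the index date can serve as a control.
2. Add the clinical risk-group flag to the weekly matching or, where exact matching fails, to the Poisson model.
3. Report unmatched vaccinees by age band and risk group.
4. Reconcile the synopsis sentence, Sections 9.2.1 and 9.2.2, and the under-12 stratum in Section 9.7.2.
5. Keep health care workers and others with no identifiable route in the primary VE. The objective covers everyone with at least one dose, and removing them would change the target population. Section 9.9 already notes that NHS Digital data lack occupation; extend this to name it as an unmeasured determinant of early vaccination.

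The cost is protocol and SAP wording and one derived flag from variables already planned. The downside is slightly fewer exact matches.
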